**Study Visit 7 or Telephone Call as applicable (Day 70) (+/- 1 week)**

Collect physical examination

Collect Vital Signs measurements

Monitor severe adverse events (SAE) and adverse events (AE)

Collect Concomitant medication review

Collect Nutritional Assessment

3-day average fistula volume (3 days immediately preceding study visit)

Collect adjustment of medications and fluids if recorded

**Telephone Call 4 (Day 77) (+/- 3 days)**

Monitor severe adverse events (SAE) and adverse events (AE)

Nutritional Assessment

3-day average fistula volume (3 days immediately preceding telephone call)

Adjustment of medications and fluids if necessary

**Study Visit 8 or Telephone Call as applicable (Day 84) (+/- 1 week)**

Collect physical examination if during visit

Collect Vital Signs measurements if during visit

Chemistry Panel (sodium, potassium, chloride, bicarbonate, blood urea nitrogen, creatinine glucose)

Liver Function tests (total bilirubin, direct bilirubin, alkalkine phosphatase, alanine aminotransferase, aspartate aminotransferase, lipase, amylase)

Plasma PK (Pharmacokinetics)

- Processed according to separate “Sample Processing Procedure”

IRB Study Number: 20170189  
Version Date: June 16, 2021  
PI: [name]

NCT02889393

Serum pregnancy test  
Monitor severe adverse events (SAE) and adverse events (AE)  
Collect Concomitant medication review  
Collect Nutritional Assessment  
3-day average fistula volume (3 days immediately preceding study visit)  
Collect adjustment of medications and fluids if recorded

**Telephone Call 5 (Day 91) (+/- 3 days)**

Monitor severe adverse events (SAE) and adverse events (AE)  
Nutritional Assessment  
3-day average fistula volume (3 days immediately preceding telephone call)  
Adjustment of medications and fluids if necessary

**Study Visit 9 or Telephone Call as applicable (Day 98) (+/- 1 week)**

Collect physical examination  
Collect Vital Signs measurements  
Monitor severe adverse events (SAE) and adverse events (AE)  
Collect Concomitant medication review  
Collect Nutritional Assessment  
3-day average fistula volume (3 days immediately preceding study visit)  
Collect adjustment of medications and fluids if recorded

**Telephone Call 6 (Day 105) (+/- 3 days)**

Monitor severe adverse events (SAE) and adverse events (AE)  
Nutritional Assessment  
3-day average fistula volume (3 days immediately preceding telephone call)  
Adjustment of medications and fluids if necessary

**Study Visit 10, End of Treatment (EOT), (Day 112) (+/- 1 week)**

Collect physical examination  
Collect Vital Signs measurements  
Chemistry Panel (sodium, potassium, chloride, bicarbonate, blood urea nitrogen, creatinine glucose)  
Liver Function tests (total bilirubin, direct bilirubin, alkalkine phosphatase, alanine aminotransferase, aspartate aminotransferase, lipase, amylase)  
Plasma PK (Pharmacokinetics)

- Processed according to separate "Sample Processing Procedure"

Serum pregnancy test  
Monitor severe adverse events (SAE) and adverse events (AE)  
Collect Concomitant medication review  
Collect Nutritional Assessment  
3-day average fistula volume (3 days immediately preceding study visit)  
Collect adjustment of medications and fluids if recorded  
Fistula closure (y/n)  
Complete Questionnaires (see additional documents)

IRB Study Number: 20170189  
Version Date: June 16, 2021  
PI: [name]

NCT02889393

**Study Visit 11, Long-Term Follow-up Visit, 3 months after EOT (-2 weeks/+3 months)**

Monitor severe adverse events (SAE) and adverse events (AE)

Collect Concomitant medication review

Collect Nutritional Assessment

Chemistry Panel (sodium, potassium, chloride, bicarbonate, blood urea nitrogen, creatinine glucose)

Liver Function tests (total bilirubin, direct bilirubin, alkalkine phosphatase, alanine aminotransferase, aspartate aminotransferase, lipase, amylase)

Plasma PK (Pharmacokinetics)

- Processed according to separate "Sample Processing Procedure"

3-day average fistula volume (3 days immediately preceding study visit)

Fistula closure (y/n)

Complete Questionnaires (see additional documents)

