### **Enrollment within 2 months of signing consent**

Inclusion/Exclusion criteria

Vital signs measurements

Nutritional assessment

3-day average fistula output

Complete questionnaires (see additional documents):

1. ASCQ-Me Short Form v2.0 - Social Functioning Impact
2. ASCQ-Me v2.0 - Sleep Impact Short Form

IRB Study Number: 20170189  
Version Date: June 16, 2021  
PI: [name]

NCT02889393

3. Global Health Scale v1.2
4. PROMIS Scale v1.0 - GI Belly Pain
5. PROMIS Scale v1.0 - GI Diarrhea
6. PROMIS Scale v1.0 - GI Nausea and Vomiting
7. PROMIS SF v2.0 - Ability to Participate

Teaching of self-administration of medication

After study enrollment, the subject will be randomly assigned (by a computerized method, using the site 'www.sealedenvelope.com') to begin teduglutide treatment immediately or to continue standard of care (SOC) treatment. The randomization will be performed by a member of the study that is not involved in the informed consent process, and will be enclosed in sequentially numbered opaque envelopes. The envelopes will be given to the PI prior to the enrollment visit. At study visit 5 (day 56), the subject will then cross-over to the opposite treatment assignment. The half-life of teduglutide is 2-3 hours. During the period the subjects are on the "SOC only" treatment arm, the subjects will be given the option to replace some Study visits with Telephone Calls for their convenience. If study visits overlap due to the time window, either visit may be skipped or completed on the same day. Please see information below, and the Study schema.

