**Drug Administration, Dispensation and Disposition**

Once consent is obtained and necessary baseline data collected, the subject will begin receiving teduglutide (0.05 mg/kg/d, for moderate renal impairment defined as serum

IRB Study Number: 20170189  
Version Date: June 16, 2021  
PI: [name]

NCT02889393

creatinine > 1.5 times the upper limit of normal, the dose will be reduced to 0.025 mg/kg/d, administered once daily subcutaneously into the abdomen, thigh, or arm (at approximately the same time each day) for 8 weeks. For enrolled subjects demonstrating a favorable trend and are deemed to be reliable (both as determined by the PI) but still have a fistula at the end of treatment (EOT) or long-term follow-up, the subject will be offered an “open-label” extension whereby they will continue to receive teduglutide at the previous dose for up to another 12 months or permanent fistula closure, whichever occurs first.

Immediately prior to initiating the 8-week period of drug administration, the subject will receive training on how to safely reconstitute and administer the medication. The volume of reconstituted study drug to be administered is a fixed dose of 0.005 mL/kg body weight. Each day, the injection site should be changed. The subject should be dosed at approximately the same time each day. If a subject forgets to take drug, that day’s dose should be administered as soon as possible, even if this is later in the day or evening. Consecutive doses should be separated by approximately 12 hours. Dates of days with missed or incomplete doses are to be reported in the diary. The subject is going to be instructed to bring back all used and unused IP. The IP will then be disposed of per pharmacy SOP. University of Miami Research Pharmacy will be receiving, storing, dispensing, keeping inventory, and disposing the IP for this study as per their standard operating procedures.

Study drug will be packaged, labeled, and delivered to the clinical center by the sponsor or designee. Each study drug kit will contain labeling with the general dosage instructions, storage conditions, expiration date, kit number, and company name. All medication supplied to be used in this study will be manufactured, tested, labeled, and released according to current legal requirements and Good Manufacturing Practice (GMP). Ancillary supply kits containing syringes with needles for injection and reconstitution, sterile water, and alcohol swabs will also be provided.

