#### **Data Fields**

Age

BMI

Gender

Charlson Comorbidity Index

Questionnaires (see additional documents)

Cause of major intestinal resection: trauma, emergency operation, elective operation, inflammatory bowel disease, other

Location of fistula: stomach, duodenum, jejunum, ileum, colon

Days since last operation

Days since fistula diagnosis

Type of nutrition: per os (PO), enteral nutrition (EN), parenteral nutrition (PN), PO + EN, PO + TPN, EN + PN, PO +EN + PN

IRB Study Number: 20170189  
Version Date: June 16, 2021  
PI: [name]

NCT02889393

Concomitant medications: antidiarrheals, antisecretory agents  
3-day average fistula volume (continuous variable)  
Output of fistula >500 mL/day (Y/N)

Because of the expected increase in luminal absorption, subjects will be closely monitored for increased oral medication absorption, particularly opioids and sedating medications. Subjects will be assessed for pinpoint pupils and lethargy. If clinical evidence of increased oral medical absorption is discovered, the doses will be accordingly decreased. If clinical evidence of fluid overload is discovered (such as breathlessness, subjective dyspnea, new-onset pitting peripheral edema, change in body weight, jugular venous distention, and rales on lung auscultation), then EN and PN prescription will be decreased accordingly.

Additionally, subjects will be monitored for clinical evidence of volume depletion. Clinical signs suggestive of volume depletion include dry mucus membranes, poor skin turgor, decreased urine output, or rapid body weight loss.

Fluid and volume status will be assessed according to the usual clinical signs and symptoms: breathlessness, subjective dyspnea, new-onset pitting edema, change in body weight, and rales on lung auscultation. This will be assessed both in person at the time of study visit as well as by self report from the subject during phone calls.

Criteria for discontinuation of teduglutide in patients who experience fluid overload include: decrease in room-air oxygen saturation > 5% from baseline, significant worsening of peripheral edema resulting in functional limitation, severe dyspnea resulting in functional limitation, and hospitalization for congestive heart failure.

Data will be de-identified and stored on password-protected network accessible only to research staff. Data will be retained for at least six years following conclusion of the study on this network.

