Intestinal obstruction occurred in 3.9% (n=6) of patients receiving teduglutide in the prior studies, with an onset between 6 days and 19 months. Only 1 patient required surgical intervention. Subjects will be monitored clinically for signs and symptoms of GI obstruction. For those patients who develop obstruction, teduglutide will be temporarily discontinued while the patient is clinically managed and restarted when the obstructive presentation resolves, if clinically indicated.

Biliary symptoms of cholecystitis and gallstones/sludge occurred in 7.5% (n=13) of patients in previous teduglutide studies, though almost half of them had a history of biliary disease prior to enrollment. None of the biliary events necessitated study withdrawal.

Pancreatitis developed in 1.7% (n=3) of all teduglutide-treated patients in previous trials, though all three patients had a history of pancreatitis prior to enrollment. None of the events required study withdrawal.

Fluid overload developed in 13.3 % (n=23) of all teduglutide-treated patients in pooled Phase III studies. Subjects will be closely monitored for increased oral medication absorption, particularly opioids and sedating medications. Subjects will be assessed for pinpoint pupils and lethargy. If clinical evidence of increased oral medical absorption is

IRB Study Number: 20170189  
Version Date: June 16, 2021  
PI: [name]

NCT02889393

discovered, the doses will be accordingly decreased. If clinical evidence of fluid overload is discovered (such as breathlessness, subjective dyspnea, new-onset pitting peripheral edema, change in body weight, and rales on lung auscultation), then EN and PN prescription will be decreased accordingly.

During weekly assessments, if the patient is on PN and there are clinical signs or suspicion of fluid overload, the PN volume will be decreased by 10% to 30% in coordination with the PN Pharmacy. We will then continue monitoring and adjust PN/IV volume accordingly to maintain clinical nutrition and volume status.

Criteria for discontinuation of teduglutide in patients who experience fluid overload include: decrease in room-air oxygen saturation > 5% from baseline, significant worsening of peripheral edema resulting in functional limitation, severe dyspnea resulting in functional limitation, and hospitalization for congestive heart failure.

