### **Procedures for Reporting Adverse Events**

Adverse events may be spontaneously reported, obtained through non-leading questioning, or noted during examination of a subject. Adverse events will be recorded from the signing of informed consent through the last dose of study drug. Serious adverse events will be recorded from the signing of informed consent through 30 days after the last dose of study drug.

At each visit, new AEs are recorded sequentially on the Adverse Event log. The AE term will note the diagnosis whenever possible, not the individual signs or symptoms (eg., myocardial infarction will be recorded rather than chest pain, elevated cardiac enzymes, and abnormal ECT). Also recorded are:

- Start and stop date and time
- Whether or not the event is continuing
- Frequency (intermittent, continuous)
- Intensity (mild, moderate, severe)
  - Mild: usually transient, requiring no special treatment and generally not interfering with usual daily activities
  - Moderate: usually ameliorated by simple therapeutic maneuvers and impairs usual activities
  - Severe: requires vigorous therapeutic intervention and interrupts usual activities. Hospitalization may or may not be required.
- Relationship to study drug (not related, related): identify relationship as “related” if a causal relationship between the investigational product and an AE is at least a reasonable possibility (i.e. the relationship cannot be ruled out).
- Whether or not the AE is serious (i.e. an SAE). If identified as an SAE, the AE will be reported as an SAE.
- Actions taken (none, study drug dose interrupted, study drug discontinued, other medication change, non-drug therapy, change in parenteral nutrition or IV fluids).
- Outcome (resolved, severity or frequency increased, ongoing, fatal). An individual AE receives only one outcome.

IRB Study Number: 20170189  
Version Date: June 16, 2021  
PI: [name]

NCT02889393

Adverse events not resolved at the end of treatment will be followed until resolution or until the AE is judged by the investigator to have stabilized.

✓

Laboratory values, blood pressure, ECG evaluations, and clinical findings at the scheduled physical examinations will be reported as AEs if they:

- Are considered clinically significant by the investigator
- Fulfill SAE criteria, and/or
- Cause subject discontinuation from the study

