	Open-Label Extension (up to 12 additional Study Visits and 12 additional Telephone Calls)		
	Extension Study Visit 1 +/- 1 week	Extension Study Telephone Call 1 to End ± 4 d	Extension Study Visit 2 to End +/- 1 week
Informed Consent	X		
Collect Complete Physical Exam Results A	X		X
Collect vital signs measurements B	X		X
Self-administration of medication and teaching if needed	X	X	X
IP Dispensation and Accountability	X		X
Collect chemistry panel results **	X		X
Collect liver function test results **	X		X
Collect serum pregnancy test (if applicable)	X		X
Monitor SAE/AE C	X	X	X
Collect concomitant medication review	X	X	X
Nutritional assessment D	X	X	X
Approx. average daily fistula output	X	X	X
Questionnaires			X F

A. A complete physical examination during an applicable study visit will include an assessment as per clinical judgement.

B. Vital sign measurements during an applicable study visit will include body temperature, heart rate, respiratory rate, and blood pressure. Height will be obtained at Screening only; weight will be measured at screening and during applicable study visits.

C. Patients will be monitored for non-serious adverse events and serious adverse events from the time when informed consent is obtained at Screening up to and including 30 days for SAEs and through the Long Term Follow Up (Study Visit 11) for AEs.

D. May include adjustment of parenteral nutrition (PN) volume as per pre-defined weaning protocol.

E. IP accountability only at visit 10

F. Questionnaires for the Open-Label Extension Study will only be administered at the End of the study

\* PK = Pharmacokinetics, processed according to separate "Sample Processing Procedure"

\*\* Laboratory test results for the Open-Label Extension Study may be collected every 3 months if completed clinically

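### SOC-first subjects who do not enter the extension at Visit 10 have no scheduled study contact in the 30-day post-dose SAE window, whereas teduglutide-first subjects have four nominal contacts in theirs

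*Combined protocol and SAP*

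**What the plan says.** **Timing of the last dose.** The enrollment section states: "At study visit 5 (day 56), the subject will then cross-over to the opposite treatment assignment". The drug administration section has the drug given once daily ("at approximately the same time each day) for 8 weeks"). The end-of-treatment visit is "Study Visit 10, End of Treatment (EOT), (Day 112) (+/- 1 week".

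**Next contact.** For a subject not in the extension, the only later entry in the schedule is "Study Visit 11, Long-Term Follow-up Visit, 3 months after EOT (-2 weeks/+3 months". It lists SAE/AE monitoring, medication review, nutritional assessment, chemistry and liver panels, PK, fistula output, closure and questionnaires. Neither the visit text nor Appendix E lists a physical examination or vital signs there.

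**Recording periods.** Section 9, Procedures for Reporting Adverse Events, says: "Serious adverse events will be recorded from the signing of informed consent through 30 days after the last dose of study drug". The Serious Adverse Events subsection repeats this. For non-serious AEs, section 9 stops recording at the last dose. Footnote C of Appendix E instead has monitoring run "up to and including 30 days for SAEs and through the Long Term Follow Up (Study Visit 11) for AEs".

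**Fluid status.** The Data Fields part of section 6 says: "Additionally, subjects will be monitored for clinical evidence of volume depletion". It describes assessment of fluid and volume status in person at study visits and by self-report on phone calls. Section 8 provides that, when fluid overload is suspected at a weekly assessment of a subject on PN, "the PN volume will be decreased by 10% to 30% in coordination with the PN Pharmacy", with monitoring and adjustment to continue afterwards.

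**The concern.** Safety is the first-named objective, and only 10 subjects are planned. The plan sets a 30-day post-dose period for SAEs, but for one of the two sequences it schedules nobody to ask during that period. Post-drug safety information is therefore gathered by two different methods, depending on randomized order: repeated near-weekly questioning in one sequence and a single late question in the other. With about five subjects per sequence, one missed or misdated admission would visibly change the summary.

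The events in question are ones the plan expects. The section on events necessitating withdrawal says that readmission for fistula-related complications, with dehydration among the examples, is common and likely during both treatment and follow-up. Withdrawal of a drug that raises absorption, possibly after PN has been reduced, is a time when volume depletion would be of interest. The scheduled occasions for detecting it end at Day 112.

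**Working it through.** The plan gives no figure to reproduce. The check is date arithmetic on the visit schedule, for subjects who complete 8 weeks of dosing.

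**Last dose**
- Teduglutide-first: about Day 0 + 56 = Day 56.
- SOC-first: about Day 56 + 56 = Day 112 (Visit 10).

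**Gap from last dose to Visit 11, SOC-first, not in the extension** (assumption: 3 months = 91 days)
- Earliest: 91 − 14 = 77 days.
- Nominal: 91 days.
- Latest: 91 + 91 = 182 days.

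Sensitivity of the gap:

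| Convention | Earliest | Latest |
|---|---|---|
| 3 months = 91 days | 77 | 182 |
| 30-day months | 76 | 180 |
| Calendar months | 75 to 78 | 181 to 184 |
| Visit 11 dated from nominal Day 112, Visit 10 moved by 7 days | 70 | 189 |

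Even the shortest reading, 70 days, lies 70 − 30 = 40 days beyond the SAE window.

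**Delay from close of the SAE window to Visit 11** (91-day convention)
- Earliest: 77 − 30 = 47 days.
- Nominal: 91 − 30 = 61 days.
- Latest: 182 − 30 = 152 days.

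**Scheduled contacts within 30 days of the last dose**
- Teduglutide-first, Days 57 to 86: Days 63, 70, 77 and 84, that is 7, 14, 21 and 28 days after the last dose. Nominal count 4. Day 84 also carries chemistry and liver panels.
- SOC-first, Days 113 to 142: none. Count 0.

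The count of 4 is approximate. With windows applied, Day 63 (±7) spans Days 56 to 70, Day 70 (±7) spans 63 to 77, Day 77 (±3) spans 74 to 80, and Day 84 (±7) spans 77 to 91. Only the Day 70 and Day 77 contacts must fall inside Days 57 to 86. The enrollment section also lets either of two overlapping visits be skipped.

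**Subjects affected.** Assuming equal allocation, 10 / 2 = 5 are SOC-first. Those who enter the extension at Visit 10 drop out of the count, because they stay on drug and are contacted about every 2 weeks. The documents give no rate of entry, so the range is 0 to about 5.

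**The case against.** The strongest reply is that these subjects are neither out of sight nor unasked.

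- Visit 11 does ask about SAEs and AEs and includes a nutritional assessment and chemistry panel. Section 9 also accepts spontaneous reports.
- AEs unresolved at end of treatment, and persistently abnormal laboratory results, are followed to resolution (or, for AEs, until stable).
- Subjects come from the Surgical Nutrition service, and those on PN have blood tests in routine care.
- Section 8 says monitoring continues after a PN reduction.
- Favorable but incomplete responders may go straight into the extension.
- No safety comparison by sequence is planned, and 10 subjects could not support one.

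Much of this stands, and it rules out the stronger readings a reader might infer. The documents do not show that subjects have no contact at all, only no scheduled study contact. They do not show that serious events go unsought, only that they are not actively solicited during the window. They do not say that fluid status is assessed exclusively at visits and calls. They do not establish that SOC-first safety will look better, only that it may.

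The reply does not close the gap. Recall at Visit 11 comes at least 47 days after the window ends and cannot find a transient episode in time. The follow-up rules cover events and laboratory abnormalities already present, not new ones. The continued monitoring in section 8 sits under weekly assessments, whose schedule ends at Day 112. No frequency is given for routine care, and section 8 itself says that for subjects not on PN the study blood draws are additional. Extension entry needs a favorable trend, a persisting fistula and a judgement of reliability by the principal investigator, and it may come only at long-term follow-up, after the gap.

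**Conclusion.** The point holds for SOC-first subjects who stop at about Day 112 and do not enter the extension then. They have 0 scheduled study contacts in the 30-day SAE window, against 4 nominal contacts for teduglutide-first subjects. Their next contact is 77 to 182 days after the last dose. Post-drug ascertainment therefore differs by sequence and may look more favourable in SOC-first subjects. The volume-depletion monitoring described in section 6 has no scheduled occasion in the same gap.

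The size rests on three assumptions: 3 months equals 91 days, allocation is equal (at most about 5 of 10 affected), and dosing runs the full 8 weeks. The first barely matters, since every convention leaves the 30-day window empty. The number at specific risk after a PN reduction is smaller still and cannot be estimated from the documents. This is an inexpensive improvement to a pilot's safety data. It does not undermine the trial.

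**What to change.** 1. For subjects whose last dose is at about Day 112 and who do not enter the extension at that point, add one telephone call about 30 days after the last dose (112 + 30, about Day 142). Use the existing Telephone Call checklist. An earlier call is optional.
2. Mark the call in Appendix E and in the visit list.
3. State in section 7 that post-drug SAEs are reported over the same 30 days after the last dose in both sequences.
4. Reconcile section 9, which ends AE recording at the last dose, with footnote C of Appendix E, which runs it through Visit 11. Otherwise a non-serious event found on the new call would be recorded under one passage and not under the other.

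Cost: up to 5 calls, or up to 10 with the optional earlier one, made by existing staff, plus a schedule line and slight subject burden. No dose or clinical rule changes.
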